**Table 11: Schedule of Assessments: Extension Period and Early Termination: Cohort 4**

| Period  | Extension                        |     |        |     |     |     |        |     |     |      |        |      |      |      |        |      |      |      |        |      | ET  |      |      |
|---|----------------------------------|-----|--------|-----|-----|-----|--------|-----|-----|------|--------|------|------|------|--------|------|------|------|--------|------|-----------------|------|------|
|   | Year 1                           |     | Year 2 |     |     |     | Year 3 |     |     |      | Year 4 |      |      |      | Year 5 |      |      |      | Year 6 |      |                 |      |      |
| Study Day                                     | 281                              | 365 | 449    | 533 | 617 | 701 | 785    | 869 | 953 | 1037 | 1121   | 1205 | 1289 | 1373 | 1457   | 1541 | 1625 | 1709 | 1793   | 1877 | 1961            | 2045 | 2129 |
| Window (day)                                  | ±5                               | ±5  | ±5     | ±5  | ±5  | ±5  | ±5     | ±5  | ±5  | ±5   | ±5     | ±5   | ±5   | ±5   | ±5     | ±5   | ±5   | ±5   | ±5     | ±5   | ±5              | ±5   | ±5   |
| ALXN1210 administration                       | X                                | X   | X      | X   | X   | X   | X      | X   | X   | X    | X      | X    | X    | X    | X      | X    | X    | X    | X      | X    | X               | X    |      |
| PNH clone size                    |                                  | X   |        | X   |     | X   |        | X   |     | X    |        | X    |      | X    |        | X    |      | X    |        | X    |                 | X    |      |
| Pregnancy test                    | X                                | X   | X      | X   | X   | X   | X      | X   | X   | X    | X      | X    | X    | X    | X      | X    | X    | X    | X      | X    | X               | X    | X    |
| PNH symptomatology                | X                                | X   | X      | X   | X   | X   | X      | X   | X   | X    | X      | X    | X    | X    | X      | X    | X    | X    | X      | X    | X               | X    | X    |
| Physical examination                          |                                  |     |        |     |     |     |        |     |     |      |        |      |      |      |        |      |      |      |        |      |                 |      | X    |
| Abbreviated physical examination  | X                                | X   | X      | X   | X   | X   | X      | X   | X   | X    | X      | X    | X    | X    | X      | X    | X    | X    | X      | X    | X               | X    |      |
| Vital signs                                   | X                                | X   | X      | X   | X   | X   | X      | X   | X   | X    | X      | X    | X    | X    | X      | X    | X    | X    | X      | X    | X               | X    | X    |
| 12-Lead ECG                       |                                  |     |        |     |     |     |        |     |     |      |        |      |      |      |        |      |      |      |        |      |                 |      | X    |
| Chemistry, including LDH                      | X                                | X   | X      | X   | X   | X   | X      | X   | X   | X    | X      | X    | X    | X    | X      | X    | X    | X    | X      | X    | X               | X    | X    |
| Hematology                        | X                                | X   | X      | X   | X   | X   | X      | X   | X   | X    | X      | X    | X    | X    | X      | X    | X    | X    | X      | X    | X               | X    | X    |
| Coagulation                                   | X                                | X   | X      | X   | X   | X   | X      | X   | X   | X    | X      | X    | X    | X    | X      | X    | X    | X    | X      | X    | X               | X    | X    |
| Urinalysis and urine chemistry                | X                                | X   | X      | X   | X   | X   | X      | X   | X   | X    | X      | X    | X    | X    | X      | X    | X    | X    | X      | X    | X               | X    | X    |
| PK sampling                      | X                                |     | X      |     | X   |     | X      | X   | X   | X    |        | X    |      | X    |        | X    |      | X    |        | X    |                 | X    | X    |
| Serum PD panel                   | X                                |     | X      |     | X   |     | X      | X   | X   | X    |        | X    |      | X    |        | X    |      | X    |        | X    |                 | X    | X    |
| Immunogenicity (ADA)             | X                                |     | X      |     | X   |     | X      | X   | X   | X    |        | X    |      | X    |        | X    |      | X    |        | X    |                 | X    | X    |
| QoL assessments                               | X                                |     | X      |     | X   |     | X      |     |     | X    |        | X    |      | X    |        | X    |      | X    |        | X    |                 | X    | X    |
| Infusion site evaluation         | X                                | X   | X      | X   | X   | X   | X      | X   | X   | X    | X      | X    | X    | X    | X      | X    | X    | X    | X      | X    | X               | X    |      |
| VAS for infusion site pain       | X                                | X   | X      | X   | X   | X   | X      | X   | X   | X    | X      | X    | X    | X    | X      | X    | X    | X    | X      | X    | X               | X    |      |
| Review safety card                            | ← ← ← Review continuously → → →  |     |        |     |     |     |        |     |     |      |        |      |      |      |        |      |      |      |        |      |                 |      |      |
| Concomitant medications                       | ← ← ← Monitor continuously → → → |     |        |     |     |     |        |     |     |      |        |      |      |      |        |      |      |      |        |      |                 |      |      |
| Adverse events                                | ← ← ← Monitor continuously → → → |     |        |     |     |     |        |     |     |      |        |      |      |      |        |      |      |      |        |      |                 |      |      |

Abbreviations: ADA = antidrug antibody; ECG = electrocardiogram; ET = early termination; LDH = lactate dehydrogenase; PD = pharmacodynamic; PK = pharmacokinetic; PNH = paroxysmal nocturnal hemoglobinuria; QoL = quality of life; VAS = visual analog scale

 The ET visit should only be performed for patients who discontinue or are withdrawn early from the study.

 Beginning on Day 953, patients in Cohort 4 will switch from the 10 mg/mL ALXN1210 unit dose formulation to the 100 mg/mL ALXN1210 unit dose formulation, while remaining on their current dose regimen.

-  The final dose of study drug will be administered on Day 2045.
-  Red blood cell clone size only during the Extension Period.
-  Female patients of childbearing potential only. Serum pregnancy test at end of study (Day 2129) or ET visit only; urine pregnancy test at all other time points. A negative urine test result is required prior to administering ALXN1210 to female patients on dosing days.
-  Investigator assessment of the following events: fatigue, abdominal pain, dyspnea, dysphagia, chest pain, and erectile dysfunction. Symptoms of disease burden will be captured through the QoL questionnaires.
-  Abbreviated physical examination consists of a body system relevant examination based upon Investigator judgment and subject symptoms.
-  Obtain triplicate 12-lead ECGs during the end of study (Day 2129) or at ET visit.
-  Assessment for safety as well as the following parameters as secondary endpoints: free hemoglobin, haptoglobin, reticulocyte count, and D-dimer.
-  Please refer to [Table 17](#) for cohort-specific sampling time points.
-  To include serum for exploratory PD assays; please refer to [Table 17](#) for cohort-specific sampling time points.
-  Immunogenicity samples will be collected predose on dosing days. Please refer to [Table 18](#) for cohort-specific sampling time points.
-  An induration or reaction of < 10 mm will not be listed as an adverse event unless it persists for more than 24 hours, at which time the patient must inform the study staff immediately and proceed to the nearest hospital emergency department.
-  Patient should assess infusion site pain using a 100 mm VAS. The VAS should be completed as soon as practical after completion of the infusion.

## 8. SELECTION AND WITHDRAWAL OF PATIENTS

### 8.1. Patient Inclusion Criteria

Patients must meet all of the following inclusion criteria in order to be eligible for the study:

1. Male or female patients  $\geq 18$  years of age
2. PNH diagnosis confirmed by documented high-sensitivity flow cytometry (RBCs and/or granulocytes)
3. Mean LDH  $\geq 3 \times$  upper limit of normal, based on 2 measurements from separate blood samples collected at least 1 day apart during screening
4. Willing and able to give written informed consent and comply with the study visit schedule
5. Documented meningococcal vaccination not more than 3 years prior to dosing
6. Female patients who consider themselves postmenopausal must provide evidence at screening of menopause status, based on a combination of amenorrhea for at least 1 year and increased serum follicle-stimulating hormone level ( $> 30$  IU/L) on at least 2 occasions (eg, in the absence of hormone replacement therapy, dietary phytoestrogens) or estradiol concentration  $< 10$  pg/mL.
7. Female patients of childbearing potential must use highly effective contraception as defined below, starting at screening and continuing until at least 8 months after the last dose of ALXN1210. Highly effective contraceptive methods are as follows:
  - a. Combined (estrogen and progestogen) hormonal contraception associated with inhibition of ovulation:
    - Oral
    - Intravaginal
    - Transdermal
  - b. Progesterone-only hormonal contraception associated with inhibition of ovulation
    - Oral
    - Injectable
    - Implantable
  - c. Intrauterine device
  - d. Intrauterine hormone-releasing system
  - e. Bilateral tubal occlusion
  - f. Vasectomized partner, provided that the partner is the patient's sole sexual partner
  - g. Sexual abstinence, defined as refraining from heterosexual intercourse during the entire period of risk associated with the study treatments; reliability of sexual abstinence needs to be evaluated in relation to the duration of the clinical trial and the preferred and usual lifestyle of the subject

- h. Combination of male condom with appropriate barrier methods for the female patient (double barrier methods)
8. Male patients with a female spouse/partner of childbearing potential or a pregnant or breastfeeding spouse or partner must agree to use barrier contraception (male condom) during the Treatment Period and for at least 8 months after the last dose of ALXN1210. Barrier contraception is required even with documented medical assessment of surgical success of a vasectomy. Female spouses/partners of male patients who are of childbearing potential must use highly effective contraception (as defined in inclusion criterion #7) or acceptable contraception, as defined below, starting at screening and continuing until at least 8 months after the last dose of ALXN1210. Male patients must not donate sperm during the Screening and Treatment Periods and for at least 8 months after the last dose of ALXN1210.

Acceptable contraceptive methods are as follows:

- a. Simultaneous use of male condom and appropriate barrier methods for the female partner

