- Fifteen days after the second patient in Cohort 3 receives the first maintenance dose to determine whether Cohort 4 can be opened.
- Approximately 7 days after the second patient in Cohort 4 receives the 3000 mg dose to review safety.
- Approximately 7 days after the second patient in Cohort 4 receives the first 5400 mg dose to review safety.

If additional patients are screened and are eligible for enrollment before a dose-escalation decision has been made by the DMC for any cohort, those patients will be assigned to the active cohort with the lowest dose level.

On Day 253, patients will continue treatment in a long-term Extension Period of the study, at the same maintenance dose and frequency as their final dose of ALXN1210 administered during the Treatment Period and receive ALXN1210 until the product is registered or approved (in accordance with country-specific regulations) or for up to 5 years, whichever occurs first. Beginning on Day 463 for patients in Cohort 2, Day 477 for patients in Cohorts 3, and Day 533 for patients in Cohort 1, patients will switch from their current dose regimen to a q8w, weight-based regimen, as follows: 3000 mg for patients weighing  $\geq 40$  to  $< 60$  kg, 3300 mg for patients weighing  $\geq 60$  to  $< 100$  kg, and 3600 mg for patients weighing  $\geq 100$  kg. The dose regimen will not change for patients in Cohort 4. Beginning on Day 953 for patients in Cohort 4, Day 981 for patients in Cohort 3, Day 1023 for patients in Cohort 2, and Day 1037 for patients in Cohort 1, patients will switch from the 10 mg/mL ALXN1210 unit dose formulation to the 100 mg/mL ALXN1210 unit dose formulation, while remaining on their current dose regimen. This transition will reduce the number of vials needed for each infusion and the duration of the infusion.

Up to 30 days will be allowed for screening procedures. The total duration of treatment (which includes an Induction Period and a Maintenance Period) is approximately 253 days. The total duration of the Extension Period is up to approximately 5 years (Figure 1).

All patients will be monitored closely for signs of infection throughout the study. Treatment with prophylactic antibiotics will be at the discretion of the Investigator and per the site/country standard of care.

The dosing schedule is provided in Table 3 and the overall study design is presented in Figure 1.

[figure not shown]

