**Table 4: Schedule of Assessments: Induction and Maintenance Dosing During the Treatment Period: Cohort 1**

| Period                                     | Screening | Treatment                        |    |    |    |             |    |    |    |     |     |     |     |     |     |     |     |   |
|--|-----------|----------------------------------|----|----|----|-------------|----|----|----|-----|-----|-----|-----|-----|-----|-----|-----|---|
|  |           | Induction                        |    |    |    | Maintenance |    |    |    |     |     |     |     |     |     |     |     |   |
| Study Day                                  | -30 to -1 | 1                                | 7  | 15 | 22 | 29          | 43 | 57 | 85 | 113 | 127 | 141 | 169 | 197 | 211 | 225 | 253 |   |
| Window (day)                               | N/A       | ±1                               | ±1 | ±1 | ±1 | ±1          | ±1 | ±1 | ±2 | ±2  | ±2  | ±2  | ±2  | ±2  | ±2  | ±2  | ±2  |   |
| Informed consent                           | X         |                                  |    |    |    |             |    |    |    |     |     |     |     |     |     |     |     |   |
| Confirmation of meningococcal vaccination  | X         |                                  |    |    |    |             |    |    |    |     |     |     |     |     |     |     |     |   |
| Medical history and demographics           | X         |                                  |    |    |    |             |    |    |    |     |     |     |     |     |     |     |     |   |
| Virus serology                             | X         |                                  |    |    |    |             |    |    |    |     |     |     |     |     |     |     |     |   |
| PNH clone size                             | X         | X                                |    |    |    |             |    | X  |    | X   |     |     | X   |     |     |     | X   |   |
| Height, weight, BMI                        | X         | X                                |    |    |    |             |    |    |    |     |     |     |     |     |     |     |     |   |
| Pregnancy test                             | X         | X                                |    | X  |    | X           |    | X  | X  | X   |     | X   | X   | X   |     | X   | X   |   |
| PNH symptomatology                         | X         | X                                | X  | X  | X  | X           | X  | X  | X  | X   | X   | X   | X   | X   | X   | X   | X   |   |

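### As worded, the male condom duty and the sperm-donation ban in inclusion criterion 8 leave out the Extension Period, where most of the planned dosing takes place

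*Protocol*

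**What the plan says.** Protocol Section 8.1, criterion 8, sets several duties for male patients and their partners, and the synopsis repeats them.

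- **Condom.** A man whose partner is of childbearing potential, pregnant or breastfeeding "must agree to use barrier contraception (male condom) during the Treatment Period and for at least 8 months after the last dose of ALXN1210".
- **Vasectomy.** "Barrier contraception is required even with documented medical assessment of surgical success of a vasectomy". This sentence names no period.
- **Partner's contraception.** A partner of childbearing potential must use highly effective or acceptable contraception "starting at screening and continuing until at least 8 months after the last dose of ALXN1210".
- **Sperm donation.** "Male patients must not donate sperm during the Screening and Treatment Periods". The same 8-month tail is then added.

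Section 6 describes the periods. It states that "The total duration of treatment (which includes an Induction Period and a Maintenance Period) is approximately 253 days". From Day 253 patients move into the next phase: "long-term Extension Period of the study, at the same maintenance dose and frequency as their final dose of ALXN1210 administered during the Treatment Period". The Extension can last up to about 5 years and ends sooner if the product is approved.

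**The concern.** Two of the male duties are tied to a named period, and that period appears to stop at about Day 253 while dosing goes on for years. A duty that stops during dosing and then restarts for 8 months after the last dose makes no sense as a protection.

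The criterion itself shows that the condom is meant to do more than prevent conception: it is required with a pregnant or breastfeeding partner, and even after a proven vasectomy. Section 15.8 names semen as a possible route of exposure in utero and lets a man stay in the study after his partner becomes pregnant. A man in the Extension with a pregnant partner is therefore foreseeable, yet as written the condom rule does not reach him. The point concerns participant and partner protection only. Endpoints, sample size and analysis are untouched.

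**Working it through.** **Step 1. Does Treatment Period include the Extension?** The protocol keeps the two apart throughout:

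- Section 6 counts only Induction and Maintenance as treatment, about 253 days, and sets the Extension dose by reference to the final Treatment Period dose.
- The titles of Tables 4 to 7 carry the one name (for Cohort 1, "Induction and Maintenance Dosing During the Treatment Period: Cohort 1"). The titles of Tables 8 to 11 carry the other.
- The clone-size footnotes name the Treatment Period in Tables 4 to 7 and the Extension Period in Tables 8 to 11.
- Table 17 has separate Treatment and Extension rows.
- Footnotes to Tables 4 to 6 call the Day 253 dose the first Extension dose. For Cohort 4 it is Day 281 (Table 7).

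No visible text extends the condom duty or the sperm-donation ban to the Extension.

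**Step 2. How much dosing falls outside the written span?** Dose numbers are from Table 17 and final dose days from Tables 8 to 11. Where the final dose is not numbered in Table 17, it is counted on from Table 3: Cohort 1 has dose 47 on Day 2045 and so dose 48 on Day 2101.

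| Cohort | First Extension dose | Final planned dose | Extension doses / all doses | Day 253 to final dose |
|---|---|---|---|---|
| 1 | No. 11, Day 253 | No. 48, Day 2101 | 48 − 10 = 38 of 48 | 2101 − 253 = 1848 days |
| 2 | No. 8, Day 253 | No. 42, Day 2087 | 42 − 7 = 35 of 42 | 2087 − 253 = 1834 days |
| 3 | No. 7, Day 253 | No. 40, Day 2101 | 40 − 6 = 34 of 40 | 2101 − 253 = 1848 days |
| 4 | No. 5, Day 281 | No. 26, Day 2045 | 26 − 4 = 22 of 26 | 2045 − 253 = 1792 days |

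Adding up the per-patient schedules gives 129 of 156 planned doses. The literal gap is about 4.9 to 5.1 years. These are ceilings, because approval can end the Extension early, and they measure the length of the Extension, not the number of men affected.

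**Step 3. Does the span fit its own 8-month tail?** Section 6.2 gives a half-life of about 43 days (39 to 48). Eight months is 8 × 30.4375 = 243.5 days. The fraction of serum drug left is 2^(−243.5 / half-life), assuming a single-exponential decline:

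- 43 days: 243.5 / 43 = 5.66 half-lives, leaving 1.97%
- 39 days: 243.5 / 39 = 6.24 half-lives, leaving 1.32%
- 48 days: 243.5 / 48 = 5.07 half-lives, leaving 2.97%

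So both duties hold when about 2% of serum drug is left, but not, as written, while maintenance doses are being given. This says nothing about levels in semen.

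**Step 4. What is still covered?** The partner's contraception runs unbroken through the Extension, as does that of female patients under criterion 7. What lapses is the condom with a pregnant or breastfeeding partner, the condom as an added method, and the sperm-donation ban. One case of the added method is a vasectomised man, whose vasectomy alone can satisfy criterion 7f.

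**The case against.** The strongest objection is that another reading leaves no gap. If the last dose means the most recent dose, the longest Extension interval, 84 days in Cohort 4, is well short of 8 months, so no day is uncovered. This reading is possible but weak. Dosing intervals in the Treatment Period also never exceed 84 days, so naming that period would add nothing to the condom sentence once dosing had begun. Criterion 7 and the partner sentence use the same phrase for the end of all dosing. A third reading, the last dose of the Treatment Period (Day 197 to 225), would only carry cover to about Day 440 to 469 (197 + 243.5 = 440.5; 225 + 243.5 = 468.5).

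It can also be said that no site would follow the literal text, since a tail after dosing presupposes cover during dosing, and Section 15.8 assumes adequate contraception for men who continue. This supports calling it a slip. But Section 15.8 sets no duty, and a safety rule should not depend on each site guessing the intent.

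Several points stand:

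- The vasectomy sentence names no period and could be read as unlimited. That it takes its span from the sentence before it is the more natural reading, but the vasectomised-man example rests on it.
- Section 15.8 is general sponsor text. Section 4.1.3 lists only infection and immunogenicity or hypersensitivity, and no semen risk specific to ALXN1210 is shown.
- Neither the dose counts nor the serum fraction measures harm.
- The consent pages are not visible and may already cover the Extension, so it cannot be shown that any man was released from the duty.

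**Conclusion.** The concern holds. In the visible protocol, neither the condom duty nor the sperm-donation ban covers Extension dosing, which is most of the planned doses in every cohort (38 of 48, 35 of 42, 34 of 40 and 22 of 26). It is probably a drafting slip, because the partner sentence in the same criterion runs without a break.

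The practical effect is narrow. It touches only men with a pregnant or breastfeeding partner, men for whom the condom is the added method, and men who might donate sperm. Their number is not given, and the cap is 26 patients of both sexes. The conclusion rests on the protocol's consistent use of Treatment Period and on reading the last dose as the end of all dosing. Confidence is medium, because the consent text is unseen. The wording should be corrected, since it is an operative protection rule that omits most of the dosing it is meant to cover.

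**What to change.** Reword two sentences of criterion 8, in Section 8.1 and in the synopsis:

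- **Condom:** required from screening (or first dose), through the Treatment and Extension Periods, until at least 8 months after the last dose.
- **Sperm donation:** none from screening, through the Treatment and Extension Periods, until at least 8 months after the last dose.

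State separately that both duties apply to men already in the Extension, because an edited inclusion criterion does not by itself bind patients who have been enrolled. Check the consent text for the same wording and align it if needed.

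The literal gap then falls to 0 days in every cohort. The cost is a wording amendment with ethics review, which can be folded into the next amendment, and possibly re-consent of enrolled men. It adds no visit, procedure or patient, and no statistical figure changes.
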